7.4 Vital Signs

Systolic and diastolic blood pressure, pulse rate and respiratory rate should be measured in a sitting position after the participant has been resting for at least 5 minutes and by using standard clinical practice at the trial site. For remote visits, the measurements will be performed by a nurse who also performs in-home blood sample collection.

7.5 Physical examination

A physical examination will be performed during onsite visit and will include the following:

- General appearance
- Skin
- Thyroid gland
- Respiratory system
- Cardiovascular system
- Gastrointestinal system including mouth
- Central and peripheral nervous system
- Lymph node palpation

7.6 Electrocardiogram

A 12-lead ECG will be performed and interpreted locally by the investigator or delegate.

An ECG performed for any reason unrelated to the study within 7 days prior to the screening visit is acceptable provided no clinical symptoms suggestive of cardiac disease have occurred in the meantime. If the ECG was performed as a part of routine clinical practice on/before the date when the participant has signed the informed consent, it must be documented in the medical records that the reason for performing the procedure is not related to this study.

7.7 Laboratory Assessments

Local laboratories with appropriate accreditation will be used for all laboratory tests. Specific tests required at each visit are outlined in SoA (**Appendix 2**).

Fasting blood samples will be obtained at the screening and baseline visits, and at Week 1, 4, 12, 24, 36, and 48.

At these fasting visits, participants will not take any food or liquid within the last 8 hours prior to blood sampling, however water is allowed up until 2 hours prior to blood sampling. Participants can take their regular morning medications but should be advised not to take any of their diabetes medications on the

morning of their study visit. Participants should bring their diabetes medications to their study visits and take them after blood sampling.

7.8 Estimated Glomerular Filtration Rate (eGFR)

eGFR is calculated according to the MDRD equation¹³:

eGFR (ml/min/1.73m²) = 175 x (standardized sCr)^{-1.154} x (Age)^{-0.203} x (0.742 if female) x (1.212 if Black)

Where sCr is serum creatinine reported in mg/dL

7.9 Mixed Meal Tolerance Test

Following a minimum of 8-hour fast, the participant will undergo an MMTT which involves the consumption of a standardized mixed meal, consisting of 200ml of Ensure Plus and an Optifast bar with a combined calorie of 533 Cal (carbohydrate 63.4g, protein 31.8g, fat 17.4g, Fiber 6.7g), and collection of timed serial blood samples for measurement of plasma glucose, insulin and C-peptide through 180 minutes after consumption of the standardized meal (with no additional food intake during this time).

Participants will wear a CGM during the test. Prior to the test, the fasting glucose level between 70 mg/dL and 200 mg/dL will be confirmed via CGM reading or a capillary blood glucose measurement. The MMTT will only be performed if fasting glucose is within the range. If the fasting glucose is outside of this range, the test may be rescheduled once within the time window for this visit.

The participant should not take his/her glucose-lowering medications in the morning but instead bring the medications to the test. The medications should be taken after the test.

The MMTT should be performed in a laboratory with adequate emergency supplies in the event of severe hypoglycemia or severe hyperglycemia. The test should be started between 7AM and 11AM. A cannula is placed in a forearm vein. The standardized meal will be consumed within 5 minutes, and the blood samples will be collected within 15 minutes before consuming the standardized meal (ie, "0 minutes"), and at 10, 20, 30, 60, 90, 120, and 180 minutes after consumption. Blood sampling should occur as close as possible to the specified times (\pm 5 minutes) for the MMTT. After the test is completed, the participant may eat food and take his/her medications as prescribed by the investigator. Stable and acceptable glucose levels (glucose between 70-270 mg/dL over a 15 minutes) should be confirmed via CGM reading or a capillary blood glucose measurement prior to participant's discharge. For participants with glucose levels \leq 100 mg/dL, the glucose level should not be trending down in the 15-minute observation period and if it is, it should be treated until the glucose level is rising prior to discharge.

The MMTT will be performed at the time points specified in the SoA (Appendix 2). The test requires the participant to visit to the testing laboratory. If the risk of potential COVID-19 exposure overweighs the benefit of performing the test in the opinion of the Investigator, the investigator may decide not to perform this test but perform tests for HbA1c, FPG and insulin instead. Follow-up MMTT will only be scheduled in participants who had baseline MMTT data.

7.10 Test for Helicobacter Pylori

A negative urea breath test or stool antigen test for *H. pylori* is required for study inclusion. The participant should be off antibiotics, antacids, and bismuth for 2 weeks, and not be bleeding before the testing. If the test reveals the participant is positive for *H. pylori*, the participant will be treated accordingly and retested using a stool antigen test. If a stool retest is negative following completion of the treatment, the participant may be entered into the study. If, after treatment, the participant tests positive for *H. pylori* at the retest, s/he is to be excluded from the study.

7.11 Continuous Glucose Monitoring

Participants will receive a Freestyle Libre 2 CGM device and be educated on its use after their screening eligibility is confirmed. The first sensor should be placed and at least 5 days of CGM data collected within the baseline visit window. The CGM device will be placed according to the manufacture's standard instructions. Site staff will assist each participant to set up the CGM alert triggers, and train participants on how to use the reader, access and share the reports in LibreView on a computer.

Participants should be educated on not taking any supplements or medications containing high dose vitamin C (>500mg per day), including cold remedies such as Airborne® and Emergen-C® while wearing the CGM sensor.

The CGM Sensor should be removed prior to the DMR procedure. After the DMR procedure and prior to discharge, the Sensor should be placed on participants and the CGM will be used throughout the follow-up duration. The CGM data will be reviewed at each follow up visits by the treating physician for monitoring hypoglycemic events and prompting for further assessment on necessary therapeutic changes per Sections 6.2.1 and 6.2.2.

Additionally, the CGM data will be reviewed by the dietitian and participant during the lifestyle modification counseling sessions.

7.12 Endoscopic Follow-up

An endoscopic assessment will be performed at week 4 (± 7 days) post procedure. It will be performed when the benefits of performing the test outweigh the risk of potential COVID-19 exposure in the opinion of the Investigator. The procedure and peri-procedural patient care will follow site's routine practice for diagnostic upper GI endoscopy.

In case of positive findings in the treated area on endoscopy, biopsy should be performed, and the samples sent to local laboratory for histological evaluation. Further endoscopic follow up should be performed when appropriate, at a minimum one assessment at 24 weeks, to confirm resolution of any clinically significant findings. Clinically significant findings include erosions, ulcers, scalloping of the duodenal mucosa, nodularity of duodenal mucosa, patchy or diffuse erythema, patchy or diffuse petechiae, blanching or discoloration of the duodenum.

7.13 Visit Schedule

A summary of all visits and procedures can be found in SoA (**Appendix 2**). A more detailed description of each visit and accompanying procedures is described below.

7.13.1 Screening Visit – Visit 1 (within 84 days from the Index Procedure)

To limit in-person visit, the screening visit may be performed remotely. Screening BMI eligibility will be based on self-reported height and weight. Potentially eligible participants will be scheduled for laboratory tests at the study laboratory. The following procedures/assessments will be performed during this visit:

- Informed consent prior to the conduct of any study-related procedures
- Inclusion and exclusion criteria
- Demographics
- Medical history including diseases, disorders and medications
- Diabetes history including diabetes medications
- Laboratory tests:
 - o Hematology (CBC with differentials)
 - Metabolic panel (liver and renal function)
 - o Fasting serum C-peptide, FPG, HbA1C

- GAD antibodies
- o TSH
- H. Pylori (breath or stool test)
- Pregnancy test for females capable of becoming pregnant
- Registration on screening log

Once all data including testing results related to the screening have been obtained, the investigator will review the participant's eligibility for the study. If deemed eligible, participant will be scheduled for the baseline visit.

Eligible participant must meet all the inclusion criteria and none of the exclusion criteria with one exception. If a participant has met all other criteria except that s/he has been on stable glucose-lowering medication(s) for less than 12 weeks at the time of screening visit, the participant can be scheduled for baseline visit such that s/he will be on stable medication for 12 weeks at the time of baseline visit.

It is recognized that COVID-19 restrictions may cause delays in scheduling the index procedure, resulting in the screening visit being out of window. In case the screening visit is out of the visit window, the investigator will reassess the participant's eligibility by evaluating any changes in the participant's medical history and medications. The investigator may decide to repeat certain screening tests based on his/her medical judgement. If the investigator determines that the participant remains eligible for participating in the study, the participant may proceed to Baseline visit. Investigator's assessment and any repeated test results will be documented on eCRFs.

7.13.2 Baseline Visit – Visit 2 (within 21 days prior to the Index Procedure)

This visit will be performed onsite. The following evaluations/procedures are to be performed. Participant's study eligibility will be reconfirmed at this visit.

- Physical examination
- Anthropometric measurements including height, weight and waist circumference
- Vital signs
- Adverse event (changes in medical history)
- Concomitant medications
- 12-lead EKG
- Laboratory tests:
 - o Hematology (CBC with differentials)
 - Metabolic panel
 - o Glycemic parameters (HbA1C, MMTT, HOMA-IR)
 - Fasting lipid panel
 - o Lipase, Amylase
 - o Serum iron, ferritin, transferrin, saturation, serum folate, Vitamin D, Vitamin B12
 - o International normalized ratio (INR) for participants on Warfarin (may be performed on Day 0)
- H. Pylori breath or stool test
- Pregnancy test for females capable of becoming pregnant
- Assessment for eligibility
- Preparation with gastroenterologist for procedure, medication management per Section 6.
- Diabetes education, including instruction on CGM use
- Treating physician review of diabetes history and titration of glucose-lowing medications per Section 6.2
- Review CGM data
- Lifestyle counselling

If the participant is no longer eligible for the study due to a change in the participant's condition, such as pregnancy, abnormal blood test values, HbA1C outside of the protocol range, or weight change resulting in a BMI outside of the protocol range, the participant will be excluded from the study and documented as a screen failure.

The screening and baseline visit may be combined if the screening visit falls within the baseline visit window. In this case, data collected during the combined visit will serve as both screen and baseline data.

It is recognized that new COVID-19 restrictions may cause delays in scheduling the index procedure, resulting in the baseline visit out of window. In case the baseline visit is out of visit window, investigator will reassess participant's eligibility by evaluating any changes in participant's medical history and medications, Investigator's assessment will be documented on eCRF. The following tests will be repeated for safety considerations or to serve as baseline data:

- Laboratory tests:
 - Hematology (CBC with differentials)
 - o Glycemic parameters (FPG, HbA1C, insulin, HOMA-IR)
- Pregnancy test for females capable of becoming pregnant (may be performed on Day 0)
- Anthropometric measurements including weight and waist circumference (may be collected on Day
 0)
- Vital signs (may be collected on Day 0)
- International normalized ratio (INR) for participants on Warfarin (may be performed on Day 0)

7.13.3 Index Procedure Visit – Visit 3 (Day 0)

See Section 6.1 for details of the index procedure and post procedure instructions.

The following assessments/procedures will be performed.

- Handout participant study ID card
- Vital signs prior to discharge
- Concomitant medications
- Assessment of AEs
- Diabetes review and medication titration by treating physician

Participants will be instructed on transitional diet, the importance of hydration, use of CGM for the duration of the study, monitoring and preventing hypoglycemic events.

7.13.4 Follow-up Visits

Study follow up visits will be performed at Week 1, 2, 4, and every 4 weeks thereafter. The last study visit is Week 48. The visit windows and assessments/procedures to be performed at each visit are shown in SoA (**Appendix 2**).

To minimize COVID-19 risks, follow up visits may be performed remotely if necessary as below (note: "at home" denotes to participant's home or location of choice). Onsite visit is preferred and will not be considered as a protocol deviation.

- Body weight may be measured at home using the scale provided to participants
- Vital signs and waist circumference may be measured by a visiting nurse at home
- Testing samples (blood, stool, urine) may be collected by a visiting nurse at home
- Assessment of AEs, medication changes, CGM and diabetes review may be performed remotely using site's virtual visit platform
- Lifestyle modification counseling may be performed remotely at each visit.

If situation permits, visits at Week 24 and 48 should be performed onsite. However remote visits at these timepoints will not be considered as protocol deviation.

7.13.5 Unscheduled Visits

If a participant is hospitalized, seen in the emergency room, or has an unscheduled clinic visit, efforts should be made to collect the following data:

- Relevant medical history, physical examination, and laboratory test findings
- Concomitant medications
- Assessment of AEs

These assessments should be documented on the eCRFs as appropriate.

7.13.6 Premature Discontinuation

If a participant discontinues the study prematurely prior to his/her 24-week visit, to the extent possible, the participant should be scheduled for an onsite visit (V17A on SoA, Appendix 2), and the following assessments/procedures should be performed.

- Body weight, calculation of BMI, waist circumference
- Vital signs
- Concomitant medications
- Assessment of AEs that occurred since the last visit
- Hematology (CBC)
- Glycemic parameters (FPG, HbA1C, fasting insulin, HOMA-IR, MMTT)
- Metabolic panel
- Fasting lipid panel
- Serum iron, ferritin, transferrin, saturation, serum folate, Vitamin D, Vitamin B12
- CGM data
- Diabetes and medication review by treating physician
- Lifestyle modification counseling
- Study exit

If premature discontinuation is decided during a scheduled visit, the visit will be converted into a V17A and assessment procedures must be performed accordingly.

If a participant discontinues the study prematurely after his/her 24-week visit, a remote visit (R17A) should be scheduled. The following tasks will be performed.

- Concomitant medications
- Assessment of AEs that occurred since the last visit
- CGM data, if available
- Study exit

The primary reason for premature study discontinuation must be documented on the eCRF.

8 STUDY AND PARTICIPANT DISCONTINUATION

8.1 Early Study Termination

Sponsor may discontinue the study at any stage for any reason or no reason. Possible reasons for early termination may include unanticipated adverse device effects that may present unreasonable patient risk.

If the study is terminated early, the sponsor will provide a written statement describing why premature termination has occurred, and notify the investigator, IRB and the regulatory authority (if applicable). All applicable clinical study documents will be subject to the same retention policy as detailed in **Section 14.3**.

8.2 Participant Discontinuation

A participant may withdraw from the study at any time at his/her own request or may be withdrawn at any time at the discretion of the investigator for safety, behavioral, or compliance reasons.

The following events will result in terminating the participant's participation in remaining follow-up:

- Participant voluntary withdrawal
- Participant withdrawn by the investigator as clinically indicated
- Participant becomes pregnant
- Participant has symptomatic COVID19 requiring medical treatment
- Participant lost to follow-up
- Participant death

At the time of discontinuing from the study, if possible, an early discontinuation visit should be conducted. See **Section 7.13.6** for data to be collected at the time of study discontinuation.

The sponsor must be notified of the reason for participant discontinuation. The site will document this information on the electronic case report form (eCRF) and make every effort to give a full description of the reason for withdrawal. Investigator will also report this information to the EC if required per local requirements.

Participants who exit the study early will not be replaced by enrolling additional participants.

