12.3 Analysis Populations

The following analysis populations are defined for the study: Intent-to-Treat (ITT), modified Intent-to-Treat (mITT), Per-Protocol (PP) and Completed Cases (CC). The primary safety analysis will be performed on the ITT population. The primary effectiveness analysis will be performed on mITT population.

- Intent-to-Treat: The Intent-to-Treat population includes all enrolled participants as defined in Section 5.3 regardless of whether or not the participant received the full treatment.
- Modified Intent-to-Treat: The mITT population consists of the ITT population participants who received the target treatment (at least 6 cm of duodenum treatment) and that have at least one post-treatment follow-up.
- Per-Protocol: The Per-Protocol population is a subset of the mITT population and includes all participants who received the target treatment (at least 6 cm of duodenum treatment), have at least one post-treatment follow-up, do not have any major eligibility violations, and maintained stable glucose-lowering medications for 24 weeks post procedure.

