### Change = Post- Procedure value - baseline value.

- Missing data may have an impact upon the interpretation of the trial data. However, given the feasibility nature of this study, coupled with the number of patients within a Comparison Set, multiple imputation will not be attempted. The primary presentation of the results will be based on the observed data. A methodology is defined in this section for addressing missing dates.
- Date variables will be formatted as DDMMMYYYY for presentation; SAS Date9. format.
- Months will be converted to days by dividing by 30.42 and rounding up to achieve an integer value.
- SAS® Version 9.4 will be the statistical software package used for all data analyses.
- All data from this study will be presented in a listing.
- Table and listing numbering will follow ICH guidelines for post-text table and listing numbering.

For Adverse Event reporting, which includes primary and secondary variables, the primary analysis will be based on Patient counts (e.g., the number and percentage of Patients with events among the total number of Patients). The data will be presented in the format of p% (x/N) [e], with p and x being the percentage and number of Patients with events, respectively, N being the sample size of the analysis population, and e being the total number of events occurred in the x Patients. Asymptotic confidence limits will be presented based on the normal approximation to the binomial distribution for differences in proportions. Exact confidence intervals will be used for all other presentations.

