# 7.3.3. Safety Measures

Descriptive summaries for all safety measures will be based on observed data. No imputation of missing scores or observations will be implemented for safety outcomes.

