### **Primary Endpoint**

The primary endpoint of the study is predicated on safety; the distribution of this endpoint is binary. The primary population for analysis of this endpoint will be the ITT population.

Proportion of patients experiencing one or more device- or procedure-related serious adverse events at 12 weeks post-procedure.

All device-related or procedure-related serious adverse events from the start of the study procedure through relative study day 84 will be used in the tabulation.

The secondary endpoints are listed below:

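### Pregnancy or treated COVID-19 ends safety follow-up after a one-time procedure, so the 12-week related-SAE proportion can be understated if a new related SAE starts after an exit before Day 84

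*Protocol*

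**What the plan says.** Protocol 8.2 gives a list of events introduced in mandatory terms ("The following events will result in terminating the"); what they terminate is the rest of the participant's follow-up. The list includes "Participant becomes pregnant" and "Participant has symptomatic COVID19 requiring medical treatment", with no time limit within the 48 weeks. It also includes voluntary withdrawal, withdrawal by the investigator, loss to follow-up and death. The section adds: "Participants who exit the study early will not be replaced by enrolling additional participants".

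For the primary endpoint, Protocol 12.3 states "The primary safety analysis will be performed on the ITT population". SAP section 9 (Primary Endpoint) counts related SAEs "from the start of the study procedure through relative study day 84". The adverse event paragraph of SAP section 7 sets the denominator, "N being the sample size of the analysis population", and SAP 7.3.3 states "No imputation of missing scores or observations will be implemented for safety outcomes".

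Three provisions limit the loss. Protocol 7.13.6 asks for an exit visit, as far as possible, that collects AEs since the previous visit. Protocol 9.1 has related AEs followed until they resolve or stabilize. Protocol 8.3 keeps contact attempts going for people who stop attending.

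Neither document says how to count a participant with less than 84 days of observation. The sensitivity analyses of the primary endpoint in SAP 9.1 only repeat it in the FAS and PP populations.

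**The concern.** In a study with continuing treatment, an event such as pregnancy may end exposure, and follow-up is sometimes ended with it. Here the exposure is over on Day 0, while the risk that the primary endpoint measures runs on to Day 84. Ending observation for pregnancy or treated COVID-19 discards safety information that the reason for exit does not require discarding.

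With the full ITT number as denominator and no imputation, a participant who leaves in Week 3 without an event contributes to the result exactly as one observed event-free for 12 weeks. Any event missed this way can only make the device look safer. Safety is the sole primary endpoint of a first-in-human study.

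The protocol's own design also points the other way. People excluded at endoscopic screening, who never receive the device, are followed for four weeks (Protocol 4.1, 5.4). A treated participant with COVID-19 in Week 1 need not be. Remote AE assessment is already provided for because of COVID-19 (Protocol 7 and 7.13.4), so continued contact is feasible.

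**Working it through.** There is no plan figure to reproduce. The sample size is declared without a calculation (Protocol 12.2), and no event rate or exit rate is given. The SAP's group counts 3 + 7 + 10 do add to 20.

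**Step 1: what is lost.** An AE present at exit should be captured at the exit visit, and a related AE under way is followed on. What has no collection route is a related SAE that begins between exit and Day 84. Exits after Week 12 cannot affect this endpoint. Delayed onset is plausible. Protocol 1.2 reports, for a different (hydrothermal) device, three stenoses among 39 treated patients, presenting 2 to 6 weeks after the procedure; the authors of that study attributed them to early device and procedure issues that were later improved.

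**Step 2: expected size.** Let p be the true 84-day risk, d the share leaving before Day 84, and f the share of the leavers' risk that falls after exit, with exit unrelated to risk. All three are assumptions.

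Expected x/N = p(1 - d·f), so bias = -p·d·f, which is never positive.

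- p = 10%, d = 10%, f = 0.5: 10% × (1 - 0.05) = 9.5%, a bias of -0.5 points. Expected hidden events in 20 patients: 20 × 0.10 × 0.10 × 0.5 = 0.1.
- Range over p = 5 to 20%, d = 5 to 15%, f = 0.25 to 1.0: -0.06 to -3.0 points.
- Each event actually hidden moves the result by 1/20 = 5 points overall, or 1/10 = 10 points in a 10-patient group.

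**Step 3: chance of any early exit.** Suppose a share D leaves evenly over 48 weeks. Then D × 12/48 = D/4 leaves before Week 12, and the chance of at least one such exit in 20 is 1 - (1 - D/4)^20. For D = 5%, 10% and 20% this is 22%, 40% and 64%, with 0.25, 0.5 and 1.0 exits expected. On this pattern even D = 20% gives d = 5%, so d = 10% in Step 2 is generous.

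**Step 4: how far the counting rule matters.** The table shows exact (Clopper-Pearson) 95% intervals for N = 20, with x observed events and k exits before Day 84 without an event.

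| x, k | Counted as non-events, x/20 | Excluded, x/(20-k) | Counted as events, (x+k)/20 |
|---|---|---|---|
| 0, 1 | 0% (0 to 16.8) | 0/19 = 0% (0 to 17.6) | 5.0% (0.1 to 24.9) |
| 0, 2 | 0% (0 to 16.8) | 0/18 = 0% (0 to 18.5) | 10.0% (1.2 to 31.7) |
| 0, 3 | 0% (0 to 16.8) | 0/17 = 0% (0 to 19.5) | 15.0% (3.2 to 37.9) |
| 1, 2 | 5.0% (0.1 to 24.9) | 1/18 = 5.6% (0.1 to 27.3) | 15.0% (3.2 to 37.9) |
| 2, 2 | 10.0% (1.2 to 31.7) | 2/18 = 11.1% (1.4 to 34.7) | 20.0% (5.7 to 43.7) |

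With k = 0 the three columns agree.

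**Step 5: exclusion is not an unbiased repair.** A proportion among patients with an event or at least 84 days of follow-up keeps leavers who had an event and drops those who did not. On the Step 2 central inputs its numerator is 0.095 and its denominator is 0.90 + 0.10 × 0.10 × 0.5 = 0.905. The ratio is 10.5% against a true 10%: the same 0.5-point error, upward.

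**The case against.** The strongest reply is that the problem is conditional and minor. It needs both an exit before Day 84 and a new related SAE after it. The expected bias is small beside the sampling error: the exact interval for 0/20 already reaches 16.8%. No performance goal or formal hypothesis test depends on the result. SAP 8.1 accounts for early terminations with reasons, SAP 5.4 computes each patient's duration on study, and SAP listings show days relative to the procedure, so early exits can largely be identified. Voluntary withdrawal and loss to follow-up raise the same denominator question, and it is not resolved by changing the COVID-19 and pregnancy rule alone. All of this stands, and it limits the point to an inexpensive improvement.

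A reader might infer more than the documents support:

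- **That the endpoint is biased downward as a matter of fact.** The documents give no exit rate, and with no early exits there is no bias.
- **That the plan instructs early exits to be counted as event-free.** No sentence says so. It follows from the ITT denominator, the absence of imputation and the fixed window taken together. Protocol 12.4.1, which relies on available data, could be read as dropping participants of unknown status. The statement that the proportion is never overstated applies to the SAP's x/N reading.
- **That all safety information on these participants is lost.** The exit visit and the follow-up of related AEs contradict this.
- **That the rise in the upper limit from 16.8% to 19.5% measures the bias.** It shows the effect of a smaller N after discarding weeks that were observed.
- **That non-replacement adds bias.** It affects only precision.

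What the reply does not answer is that new-onset events between exit and Day 84 go uncollected for two reasons unrelated to the need for safety data, and that neither document has a rule for incomplete 84-day follow-up.

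**Conclusion.** The point holds in conditional form. The two exit rules open a gap in safety observation that the single-procedure design does not require, and the SAP's denominator turns that gap into implied non-events. The central figure of -0.5 points, and its range of -0.06 to -3.0, rest wholly on assumed risk, exit share and timing, with exit unrelated to risk. The case for acting is not the average size. It is that the error has one direction, touches the only primary endpoint, could move the result by 5 points for a single missed event, and is cheap to prevent.

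**What to change.** 1. **Protocol 8.2.** Amend so that pregnancy and treated symptomatic COVID-19 do not end safety follow-up. Continue remote SAE contact through at least Day 84 unless consent is withdrawn. This concerns data collection only, not clinical care.
2. **SAP 9.1.** For all early exits, whatever the reason, state how follow-up of less than 84 days is counted. Beside x/N, report:
   - the number with complete 84-day follow-up;
   - a Kaplan-Meier 84-day estimate, which credits the time observed but assumes that exit is unrelated to risk;
   - a bracket with event-free early exits excluded and with them counted as events. Label the excluded version as part of the bracket, not as an unbiased estimate, because it selects on outcome.

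The cost is a few remote contacts and some extra table rows, and the stated upper limit may be slightly less favourable. SAP section 3 already describes enrollment in the past tense and tabulates 20 patients. If their follow-up is finished, only part 2 can still be done.
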